5.5 Interim analyses

An interim analysis will be performed after the first 20 evaluable subjects have been observed for at least 6 cycles. If 1 or fewer treatment successes are observed in these 20 subjects, this treatment regimen will be considered inactive in this population and accrual will be terminated. If 2 or more treatment successes are observed in these 20 subjects, decisions about activity must await the final analysis. Enrollment into the study will continue while waiting for the 20th eligible subject to complete at least 6 cycles of treatment. These additional subjects will not be used to evaluate the interim stopping rule.

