5.3.2. Study Design

Subjects receiving CC-4047 alone, and the new study cohort of patients receiving CC-4047 and prednisone in combination will be evaluated using the same statistical design: a two stage design with one interim analysis will be used to permit early reporting of efficacy results if there is strong evidence that the study regimen is inactive. 37 evaluable subjects will be accrued onto this study unless undue toxicity is encountered. We anticipate accruing an additional 10-20% of subjects to account for ineligibility or cancellation; i.e. we may accrue as many as 70 subjects to this study. Subjects who have been taken off study due to toxicity related to high dose pomalidomide (i.e. those who started therapy with 3mg/day) will be replaced with new patients that will start therapy with 0.5mg/day), so that the goals of the study can be accomplished.

• Decision Rule: If 3 or fewer treatment successes are observed after all 37 evaluable subjects have been followed for at least 6 cycles, we will conclude that the treatment is insufficiently active in this subject population. If 4 or more treatment successes are observed, then this will be considered adequate evidence of promising activity, and the treatment may be recommended for further testing in subsequent studies.

- Over accrual: if more than the target number of subjects are accrued, the additional subjects will not be used to evaluate the stopping rule or used in any decision making process. However, they will be included in final point estimates and confidence intervals.
- Study duration: The anticipated accrual rate for this group of subjects is approximately 3 subjects per month. It will take approximately 14 months to accrue 37 evaluable subjects. The analysis can begin as soon as the 37th evaluable subject has been observed for 6 cycles (168 days), i.e., approximately 20 months after the trial opens.

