5.6. Sample size and power considerations

Assuming that the number of successes is binomially distributed, this decision rule has a significance level of 0.09; i.e., there is a 9% chance of finding the drug to be effective when it truly is not. The probability of declaring that this regimen warrants further studies (i.e. statistical power) under various success proportions and the probability of stopping after the first stage can be tabulated as a function of the true success proportion as shown in the following table:

If the true success proportion is	0.05	0.10	0.15	0.20	0.25
then the probability of declaring that the	0.09	0.44	0.75	0.91	0.97

regimen warrants further studies is					
And the probability of stopping at stage I	0.74	0.39	0.18	0.07	0.02
is:					

In particular, this decision rule has 91% power to detect an effective treatment given that the true response rate is at least 20% using this treatment. If the true success rate is 5%, the chance of stopping early at the first stage is 0.74 and the chance of concluding that the treatment is active is 0.09. If the true success rate is 20%, the chance of stopping early at the first stage is 0.07 and the chance of concluding that the treatment is active is 0.91 (power).

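### Does continuing enrolment while the futility interim matures defeat the purpose of the interim in the combination cohort?

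*Combined protocol and SAP*

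**What the plan says.** Section 5.3.2 puts both cohorts under one two-stage rule: "the new study cohort of patients receiving CC-4047 and prednisone in combination will be evaluated using the same statistical design". The interim is there "to permit early reporting of efficacy results if there is strong evidence that the study regimen is inactive". Stage 1 has 20 evaluable subjects and the full cohort has 37, so stage 2 has 17.

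Under section 5.5, at most 1 success in the first 20 means that "this treatment regimen will be considered inactive in this population and accrual will be terminated". The same section says what happens during the wait: "Enrollment into the study will continue while waiting for the 20th eligible subject to complete at least 6 cycles of treatment". Subjects who enter in that time do not count towards the interim rule.

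Section 5.3.2 gives the pace: "The anticipated accrual rate for this group of subjects is approximately 3 subjects per month", and "It will take approximately 14 months to accrue 37 evaluable subjects". It also allows for losses: "We anticipate accruing an additional 10-20% of subjects to account for ineligibility or cancellation". Six cycles are 168 days, and the final analysis is expected about 20 months after opening. Section 5.6 adds: "If the true success rate is 5%, the chance of stopping early at the first stage is 0.74".

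**The concern.** The wait for the 20th subject is about 5.5 months, and at 3 per month some 16 or 17 more subjects enter during it. That is nearly the whole of stage 2. A rule whose stated action is to end accrual would then have almost nobody left to turn away.

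The 0.74 chance of stopping at a 5% true rate invites the reader to expect a real saving in subjects. If the combination were inactive, most stage-2 subjects would have started it before the rule could act. Section 3.7.2 notes that thrombosis risk may rise when CC-4047 is given with steroids, so that exposure is not free. The toxicity rule in section 5.4 does not address lack of activity. The question concerns only the combination cohort: the single-agent cohort already had 3 responders among 20 (section 1.2, addendum of 3/30/11) and so had passed its interim.

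**Working it through.** **1. The plan's own figures.** Rule: stop if at most 1 of 20 succeed; promising if at least 4 of 37 succeed. With X1 ~ Bin(20, p) and X2 ~ Bin(17, p):

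- P(stop) = P(X1 ≤ 1).
- P(declare active) = sum over x ≥ 2 of P(X1 = x) × P(X2 ≥ 4 − x).

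At p = 0.05, 0.10, 0.15, 0.20 and 0.25, P(stop) is 0.736, 0.392, 0.176, 0.069 and 0.024, and P(declare active) is 0.090, 0.439, 0.751, 0.910 and 0.971. Every entry in the section 5.6 table is reproduced. None of them depends on whether accrual pauses.

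**2. Enrolment at the interim.** Follow-up is 168 / 30.44 = 5.52 months. With r evaluable subjects per month, the interim falls at 20/r + 5.52 months, with 20 + 5.52r enrolled.

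| r per month | Basis | Interim (month) | Enrolled | Left of 37 |
|---|---|---|---|---|
| 3.00 | every entrant evaluable | 12.2 | 36.6 | 0.4 |
| 2.73 | 3 / 1.1 | 12.9 | 35.1 | 1.9 |
| 2.64 | 37 / 14 | 13.1 | 34.6 | 2.4 |
| 2.40 | 3 × 0.8 | 13.9 | 33.2 | 3.8 |
| 2.00 | assumed | 15.5 | 31.0 | 6.0 |
| 1.50 | assumed | 18.9 | 28.3 | 8.7 |

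The final analysis falls at about 14 + 5.5 = 19.5 months, in line with the plan's 20. On the planned rates the interim therefore comes about 6 to 8 months sooner.

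**3. What a pause would save.** Expected enrolment with a pause at 20 is 37 − 17 × P(stop). As written, with n enrolled at the interim, it is 37 − P(stop) × (37 − n). The difference is P(stop) × (n − 20), here for n = 33.2 to 36.6.

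| True rate | P(stop) | With pause | As written | Saved by pausing |
|---|---|---|---|---|
| 5% | 0.736 | 24.5 | 34.2–36.7 | 9.7–12.2 |
| 10% | 0.392 | 30.3 | 35.5–36.8 | 5.2–6.5 |
| 15% | 0.176 | 34.0 | 36.3–36.9 | 2.3–2.9 |
| 20% | 0.069 | 35.8 | 36.7–37.0 | 0.9–1.1 |
| 36% | 0.002 | 37.0 | 37.0 | under 0.05 |

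The 36% row is the response rate that section 1.2 reports for 0.5 mg with prednisone in 22 patients. The same section gives 19% for prednisone with placebo (21 patients), and 17% (58 patients) and 15% (20 patients) for 0.5 mg alone. These are small samples, but none is near 5%.

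**4. What a pause would cost.** The mildest version pauses at the 20th evaluable subject only if 2 successes are not yet recorded, and resumes at the second. Two successes guarantee passing the interim, so the error rates do not move. The delay was simulated with 40,000 trials per setting. Assumptions: even entry at 3 per month, and lognormal response times with median 3 to 4 months and log-SD 0.5 to 0.8, truncated at 5.52 months. Means are over all trials, including those with no pause. At a true rate of 20%:

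- No confirmation lag: a pause in about 29–43% of trials, mean 0.7–0.9 months.
- Assumed lag of 1 to 2 months: a pause in about 45–85%, mean 1.0–2.2 months.
- Later responses (uniform from 2.48 to 5.52 months): mean 1.1 months without lag, 1.8–2.7 with it.

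The longest pause is about 5.5 months plus any lag. At 36% the mean is under 1 month in the lognormal settings.

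**The case for a change.** The strongest case for a change is that the plan names two effects of the interim, earlier reporting and an end to accrual, and at its own rate the second is nearly empty. At a 5% true rate, about 10 to 12 more people on average would start an inactive regimen than under a pause. A conditional pause takes one sentence, leaves 0.090 and 0.910 untouched, and rarely holds up a regimen that works as well as the earlier 36% suggests unless confirmation is slow. Saying that enrolment continues does not tell the reader how little the stop can then save.

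The arithmetic stands in full, and so does the remark about the reader: section 5.5 would be clearer with the expected enrolment at the interim. The step to a required change does not stand. Sections 5.3.2, 5.5 and 5.6 promise no smaller expected sample size. The large saving arises at the rate that the protocol's own earlier results make least likely. At the 20% target, about one subject is saved in exchange for a mean delay of roughly 1 to 2 months with a confirmation lag. A pause would also need responses adjudicated continuously and accrual stopped and restarted in a rare disease. It assumes that the 20th evaluable subject is known on the day, although some of the 10–20% allowance for ineligibility or cancellation may surface after treatment starts.

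**Conclusion.** A fair trade-off, openly stated; no change is needed. At the planned pace the combination cohort's futility stop mainly brings the conclusion forward, to about month 12 to 14 from about month 20. It spares about 0 to 4 of 17 stage-2 subjects. Significance level, power, stopping probabilities and the final decision are the same with or without a pause.

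The size depends on accrual. The 3 per month is not restated for the combination cohort. At an assumed 2 or 1.5 per month a stop would spare about 6 or 9 subjects. The addendum dates do not settle the rate. Accrual was on hold on 11/10/09, and 20 evaluable subjects had 6 cycles by 3/30/11. That is 16.6 months, or about 11 after subtracting 5.5 of follow-up, so 20 / 11 = 1.8 per month or faster, compatible with 2 as well as 3. The counts are expectations under steady entry. Time for confirmation or data cleaning would raise enrolment at the interim: counting follow-up as 6.0 months gives 34.4 to 37 (capped).

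The delay figures rest on assumed response times and an assumed confirmation lag. They show the order of the cost and are not a forecast.

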5.6. Sample size and power considerations

Assuming that the number of successes is binomially distributed, this decision rule has a significance level of 0.09; i.e., there is a 9% chance of finding the drug to be effective when it truly is not. The probability of declaring that this regimen warrants further studies (i.e. statistical power) under various success proportions and the probability of stopping after the first stage can be tabulated as a function of the true success proportion as shown in the following table:

If the true success proportion is	0.05	0.10	0.15	0.20	0.25
then the probability of declaring that the	0.09	0.44	0.75	0.91	0.97

regimen warrants further studies is					
And the probability of stopping at stage I	0.74	0.39	0.18	0.07	0.02
is:					

In particular, this decision rule has 91% power to detect an effective treatment given that the true response rate is at least 20% using this treatment. If the true success rate is 5%, the chance of stopping early at the first stage is 0.74 and the chance of concluding that the treatment is active is 0.09. If the true success rate is 20%, the chance of stopping early at the first stage is 0.07 and the chance of concluding that the treatment is active is 0.91 (power).

6 REGULATORY CONSIDERATIONS

6.1 Institutional Review Board/Ethics Committee approval

The protocol for this study has been designed in accordance with the general ethical principles outlined in the Declaration of Helsinki. The review of this protocol by the IRB/EC and the performance of all aspects of the study, including the methods used for obtaining informed consent, must also be in accordance with principles enunciated in the declaration, as well as ICH Guidelines, Title 21 of the Code of Federal Regulations (CFR), Part 50 Protection of Human Subjects and Part 56 Institutional Review Boards.

The Investigator will be responsible for preparing documents for submission to the relevant IRB/EC and obtaining written approval for this study. The approval will be obtained prior to the initiation of the study.

The approval for both the protocol and informed consent must specify the date of approval, protocol number and version, or amendment number.

Any amendments to the protocol after receipt of IRB/EC approval must be submitted by the Investigator to the IRB/EC for approval. The Investigator is also responsible for notifying the IRB/EC of any serious deviations from the protocol, or anything else that may involve added risk to subjects.

Any advertisements used to recruit subjects for the study must be reviewed and approved by the IRB/EC prior to use.

6.2 Informed consent

The Investigator must obtain informed consent of a subject or his/her designee prior to any study related procedures as per GCPs as set forth in the CFR and ICH guidelines.

Documentation that informed consent occurred prior to the subject's entry into the study and the informed consent process should be recorded in the subject's source documents. The original consent form, signed and dated by the subject and by the person consenting the subject prior to the subject's entry into the study, must be maintained in the medical records, and copy filed in the regulatory binder.

6.3 Subject confidentiality

Celgene affirms the subject's right to protection against invasion of privacy. In compliance with United States federal regulations, Celgene requires the Investigator to permit Celgene's representatives and, when necessary, representatives of the FDA or other regulatory authorities to review and/or copy any medical records relevant to the study in accordance with local laws.

Should direct access to medical records require a waiver or authorization separate from the subject's statement of informed consent, it is the responsibility of the Investigator to obtain such permission in writing from the appropriate individual.

6.4 Study records requirements

The Investigator must ensure that the records and documents pertaining to the conduct of the study and the distribution of the study drug, that is copies of eCRF and source documents (original documents, data, and records [e.g., hospital records; clinical and office charts; laboratory notes; memoranda; subject's diaries or evaluation checklists; pharmacy dispensing records; recorded data from automated instruments; copies or transcriptions certified after verification as being accurate copies; microfiches; photographic negatives, microfilm, or magnetic media; x-rays; subject files; and records kept at the pharmacy, at the laboratories, and at medico-technical departments involved in the clinical study; documents regarding subject treatment and study drug accountability; original signed informed consents, etc.]) be retained by the Investigator for as long as needed to comply with national and international regulations (generally 2 years after discontinuing clinical development or after the last marketing approval). The Investigator agrees to adhere to the document/records retention procedures by signing the protocol.

6.5 Premature discontinuation of study

6.5.1 Single center

The responsible local clinical Investigator, MDACC as well as Celgene have the right to discontinue this study at any time for reasonable medical or administrative reasons in any single center. Possible reasons for termination of the study could be but are not limited to:

- Unsatisfactory enrollment with respect to quantity or quality.
- Inaccurate or incomplete data collection.
- Falsification of records.
- Failure to adhere to the study protocol.

6.5.2 Study as a whole

Celgene and MDACC reserve the right to terminate this clinical study at any time for reasonable medical or administrative reasons.

Any possible premature discontinuation would be documented adequately with reasons being stated, and information would have to be issued according to local requirements (e.g., IRB/EC, regulatory authorities, etc.).

